8. PROTOCOL DEVIATIONS

Protocol deviations will be summarized by type of deviation and overall using counts and percentages. Two categories will be used to report protocol deviations: major protocol violations resulting in exclusion from the Per Protocol Population and minor protocol deviations. The total number of subjects with one or more major protocol violations and the total number of subjects with one or more minor protocol deviations will also be reported. Results will be presented by treatment group and overall.

9. DEMOGRAPHIC AND BASELINE CHARACTERISTICS

9.1. Recipient Demographic and Baseline Characteristics

Recipient demographic and baseline characteristics will be summarized for the AT and PP populations. Frequencies and percentages will be presented for categorical variables. Descriptive statistics (n, mean, standard deviation, median, minimum, and maximum) will be presented for continuous variables. Treatment groups will be compared statistically (chi-square test for categorical variables and two-sided, two-sample t-tests for continuous variables). Recipient demographic and baseline characteristics will also be reported for the subgroups indicated in Section 5.9 and compared statistically as noted above.

Recipient factors (history of hepatitis C and history of liver cancer), history of diabetes, type of diabetes (if present), and primary etiology of liver failure at screening will be summarized for the AT and PP populations using frequencies and percentages. This information will also be summarized for the subgroups indicated in Section 5.9.

9.2. Donor Demographic and Baseline Characteristics

Donor demographic and baseline characteristics will be summarized for the Donor Liver Population (as treated and PP). Frequencies and percentages will be presented for categorical variables. Descriptive statistics (n, mean, standard deviation, median, minimum, and maximum) will be presented for continuous variables. Treatment groups will be compared statistically (chi-square test for categorical variables and two-sided, two-sample t-tests for continuous variables). Donor demographic and baseline characteristics will also be summarized for the subgroups indicated in Section 5.9 (with the exception of MELD score) and compared statistically as noted above.

Donor medical history, reported as a history of specific medical conditions, will be summarized for the Donor Liver Population (as treated and PP) using frequencies and percentages. This information will also be summarized for the subgroups noted above.

Donor cause of death, presence of abdominal trauma at death, whether the donor is a DCD, and whether the donor experienced cardiac arrest will be summarized for the Donor Liver Population (as treated) using frequencies and percentages. This information will also be summarized for the subgroups noted above.

Liver enzymes (bilirubin, AST, ALT, GGT, alkaline phosphatase, INR, and final donor arterial lactate level) from the assessment before retrieval in the donor's abdomen, the biopsy from the assessment before instrumentation on the OCS, and liver perfusion parameters will be summarized for the Donor Liver Population (as treated) using descriptive statistics for continuous variables and frequencies and percentages for categorical variables.

10. DONOR OPERATIVE CHARACTERISTICS, OCS INSTRUMENTATION, AND OCS PERfusion

Donor operative characteristics and OCS instrumentation will be summarized using descriptive statistics for continuous variables and frequencies and percentages for categorical variables. Total cross clamp time, total ischemic time and presence of surgical complications/tears during retrieval will be summarized by treatment group. For total cross clamp time, treatment groups will be compared statistically using a two-sided, two-sample t-test.

Pre-OCS ischemic time, post-OCS ischemic time, and OCS perfusion time (in minutes) will be summarized for the OCS treatment group using descriptive statistics.

Liver enzymes (total bilirubin, AST, ALT, GGT, alkaline phosphatase, INR, and arterial lactate level) will be summarized at OCS baseline and at the OCS final. Bile volume will be summarized at the OCS final only. Both will be summarized using descriptive statistics.

The number and percentage of donor livers in the Donor Liver Population for which there was a device malfunction will also be presented.

The analyses above will be performed for the Donor Liver Population (as treated) with the exception of the device malfunction analysis, which will be performed for the Donor Liver Population (as randomized).

11. TRANSPLANT CHARACTERISTICS AND RECIPIENT POST-TRANSPLANT HOSPITAL/ICU STAY

Transplant characteristics will be summarized using frequencies and percentages for categorical variables and descriptive statistics (n, mean, standard deviation, median, minimum, and maximum) for continuous variables.

The initial post- transplant Hospital/ICU stay duration and the re-admission Hospital/ICU stay duration will be summarized using descriptive statistics.

The initial post-transplant hospital stay is defined as the duration in days from ICU admission to post transplant hospitalization discharge.

The initial post-transplant ICU stay is defined as the duration in hours from ICU admission to initial ICU clinical order discharge. If the initial ICU clinical order discharge date and time are missing, the actual ICU discharge date and time will be substituted. If the time is missing, a value of 23:59 will be used.

These analyses will be performed for the PP, mITT and AT populations.

12. ANALYSIS OF EFFECTIVENESS ENDPOINTS

12.1. Primary Effectiveness Endpoint

The primary effectiveness endpoint for this study is Early Liver Allograft Dysfunction (EAD), defined as presentation of one or more of the following criteria:

- AST level > 2000 IU/ml within the first 7 postoperative days
- Bilirubin ≥ 10 mg/dl on postoperative Day 7
- INR ≥ 1.6 on postoperative Day 7
- Primary non-functioning graft within the first 7 days (defined as irreversible graft dysfunction requiring emergency liver re-transplantation or resulting in death, in the absence of immunologic or surgical causes)

The primary hypothesis for this study is that the OCS treatment is non-inferior to the standard of care treatment with respect to this endpoint. The primary statistical hypotheses are as follows:

$$H_{10}: \pi_{1,OCS} \geq \pi_{1,CONTROL} + \delta \text{ and}$$

$$H_{11}: \pi_{1,OCS} < \pi_{1,CONTROL} + \delta,$$

where $\pi_{1,OCS}$ and $\pi_{1,CONTROL}$ are the true proportions of subjects with Early Liver Allograft Dysfunction for the OCS and standard of care treatments, respectively, and δ is the non-inferiority margin, which is here taken to be 0.075.

The primary effectiveness endpoint will be analyzed by calculating, for each treatment group, the sample proportion of subjects meeting the primary effectiveness endpoint, as well as an exact (Clopper-Pearson) 95% confidence interval for the corresponding population percentage. The 95% exact unconditional one-sided upper confidence bound based on the Farrington and Manning score statistic will be calculated for the difference between the two population proportions ($\pi_{1,OCS} - \pi_{1,CONTROL}$). An upper confidence bound less than $\delta = 0.075$ will result in rejection of the null hypothesis (H_{10}) in favor of the alternative hypothesis (H_{11}) and the demonstration of non-inferiority of OCS to control for the primary effectiveness endpoint. In the event non-inferiority is demonstrated, Fisher's exact test (two-sided) will be used to test for superiority.

This endpoint will be analyzed using the Per Protocol and mITT Populations. The Per Protocol analysis will be considered the primary analysis. Analyses will first be performed without any imputation of missing data. If there are any missing data for this endpoint, multiple imputation methods will be used for data imputation for any patients with missing values for this endpoint. The multiple imputation methods are described in Section 5.3.

Assuming the Per Protocol Population analysis of the primary efficacy endpoint with imputation of missing data results in rejection of the null hypothesis in favor of non-inferiority, a tipping point sensitivity analysis based on the Per Protocol Population as described in Section 5.4 will be used to assess the effect of missing data. A tipping point analysis will also be performed using the mITT population if the analysis of the primary efficacy endpoint with imputation of missing data based on the mITT Population results in rejection of the null hypothesis in favor of non-inferiority.

In order to examine poolability by investigational site, an analysis of the primary effectiveness endpoint including terms for treatment, MELD score, DCD donor (Yes or No), donor age (years), pooled site, and the interaction of pooled site and treatment will be performed as described in Section 5.5. This analysis will be performed for both the Per Protocol and mITT populations.

Subgroup analyses of the primary effectiveness endpoint will be performed for the subgroups indicated in Section 5.9. No data imputation or statistical tests will be performed for these subgroup analyses. In addition, analyses of the primary effectiveness endpoint by donor inclusion criteria will be performed using observed data. In these analyses, the endpoint will be reported for the proportion of subjects meeting each individual donor inclusion criteria, a single donor exclusion criteria, multiple donor exclusion criteria, and at least one donor exclusion criteria. No data imputation or statistical tests will be performed for these analyses based on donor inclusion criteria. The subgroup analyses and the donor inclusion analyses will be performed for both the Per Protocol and mITT populations.

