Randomization	After confirmation of eligibility, obtaining informed consent, and a matching donor liver is identified, potential liver transplant recipients will be randomized 1:1 to have their donor livers preserved using either the OCS Liver perfusion or the standard cold static preservation technique (Control) using cold flush and storage. Randomization will be performed through the Interactive Web Response System (IWRs). Subjects who are not transplanted with the matching donor liver will be re-randomized and treated as a new subject.
Sample Size Determination	The sample size for this trial was determined based on the effectiveness endpoint, Early Liver Allograft Dysfunction (EAD) in the first 7 days post liver

	
transplantation. The sample size calculation assumed a non-inferiority, test based on the upper bound of the Exact unconditional one-sided confidence interval for the difference in proportions using Farrington and Manning score statistic. An alpha level of 0.05, a non-inferiority margin of 0.075, a 1:1 allocation, true proportions for the primary effectiveness endpoint of 0.2 for the OCS treatment and 0.25 for the Control treatment, and power of 80%. Based on these specifications, the required sample size was determined to be 144 transplanted recipients per treatment group, or 288 total transplanted subjects. To ensure an adequate number of subjects in the Per Protocol Population, the sample size was increased to a total of 300 transplanted subjects. Subjects will be enrolled until there are either 290 subjects in the Per Protocol Population or a total of 300 transplanted subjects, whichever comes first.

Sample Size Re-estimation	A sample size re-estimation will be performed for the purpose of confirming the current sample size is sufficient for testing for non-inferiority for the primary effectiveness endpoint and to assess the feasibility of demonstrating superiority. It will be conducted after there are 200 transplanted subjects to allow for a possible upwards adjustment in sample size. The sample size will not be increased by more than 150 subjects.
Trial Sponsor	TransMedics, Inc. [name]

[figure not shown]

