3.4. Determination of Sample Size

The sample size for this trial was determined based on the primary effectiveness endpoint, Early Liver Allograft Dysfunction (EAD) in the first 7 days post-transplantation. The sample size calculation assumed a one-sided, normal approximation test for non-inferiority, an alpha level of 0.05, a non-inferiority margin of 0.075, a 1:1 allocation, true proportions for the primary effectiveness endpoint of 0.2 for the OCS treatment and 0.25 for the Control treatment, and power of 80%. Based on these specifications, the required sample size was determined to be 144 transplanted recipients per treatment group, or 288 total transplanted subjects. To ensure an

adequate number of subjects in the Per Protocol Population, the sample size was increased to a total of 300 transplanted subjects. Subjects will be enrolled until there are either 290 subjects in the Per Protocol Population or a total of 300 transplanted subjects, whichever comes first.

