5. STATISTICAL CONSIDERATIONS

5.1. General Methodology

All statistical analyses will be performed and all tables and listings will be produced using SAS® Version 9.3 or higher.

Continuous variables will be summarized using descriptive statistics, specifically the mean, median, standard deviation, minimum and maximum. Categorical variables will be summarized using frequencies and percentages. For continuous data the minimum and maximum will use the same decimal accuracy as the raw data. The mean and median will use 1 more decimal place than the raw data, and the standard deviation will use 2 more decimal place than the raw data. For categorical data, percentages will be reported to 1 decimal place. P-values will be reported to 4 decimal places. P-values less than 0.0001 will be displayed as <0.0001 in the tables.

All statistical tests will be performed at the 0.05 significance level unless otherwise noted.

All data collected will be included in the data listings. Data listings will be sorted by treatment arm and either by recipient ID or by donor ID, as appropriate.

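### Fisher's exact test for superiority is valid but conservative; an exact unconditional test, preferably Boschloo's, also holds the 5% level and has somewhat more power

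*SAP*

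**What the plan says.** SAP 12.1 sets the non-inferiority method for the EAD difference: "The 95% exact unconditional one-sided upper confidence bound based on the Farrington and Manning score statistic will be calculated for the difference". Non-inferiority holds if that bound is below 0.075. The next step is "In the event non-inferiority is demonstrated, Fisher's exact test (two-sided) will be used to test for superiority". Protocol 9.3.1 and the protocol synopsis say the same, and SAP 12.2 and protocol 9.3.2 repeat Fisher's test for the two survival endpoints. The level comes from SAP 5.1: "All statistical tests will be performed at the 0.05 significance level unless otherwise noted". No reason is given for moving from an unconditional to a conditional method.

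The trial is sized for non-inferiority only, with "an alpha level of 0.05, a non-inferiority margin of 0.075, a 1:1 allocation", EAD rates of 20% on OCS and 25% on Control, and 80% power (SAP 3.4). No effect size or power is stated for superiority. Protocol 9.7 would have let a sample size re-estimation consider superiority, with an increase of at most 150 subjects. SAP 3.5 drops that step and fixes enrolment at 300.

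**The concern.** Both steps concern the same two proportions, and the plan already accepts an exact unconditional method for the first. Fisher's test conditions on the total number of events. That makes its set of attainable p-values coarse, so its true error rate falls short of the nominal 5%. The shortfall costs power. With enrolment fixed, the choice of test is one of the few remaining ways to improve the chance of a superiority claim. That claim is the stronger of the two the plan allows, and in the secondary sequence superiority on the first survival endpoint is also the gate for superiority on the second.

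**Working it through.** **Inputs.** Planned: EAD 20% v 25%, margin 0.075, one-sided 0.05 for non-inferiority, 144 per arm required, 300 enrolled, 290 as the Per Protocol target (SAP 3.4, 3.5); two-sided 0.05 for superiority (SAP 5.1). Assumed: arm splits of 300 and 290, and OCS rates other than 20%.

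**The plan's own figure.** The SAP says "The sample size calculation assumed a one-sided, normal approximation test for non-inferiority", while the protocol synopsis names a "test based on the upper bound of the Exact unconditional one-sided confidence interval for the difference in proportions using Farrington and Manning score statistic". Under the simple normal formula, n = (1.645 + 0.842)² × (0.20×0.80 + 0.25×0.75) / (0.05 + 0.075)² = 6.18 × 0.3475 / 0.015625 ≈ 138 per arm. At 144 per arm its power is Φ(0.125/√(0.3475/144) − 1.645) = 81.6%. Full enumeration of the exact unconditional Farrington-Manning test gives 81.0% at 144. The stated 144 is reproduced closely enough under either description.

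**How far superiority is from being powered.** At 20% v 25%, two-sided 0.05 and 80% power, n = [1.960√(2×0.225×0.775) + 0.842√0.3475]² / 0.05² ≈ 1,094 per arm.

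**Superiority tests.** All 2×2 tables were enumerated for three two-sided tests:
- Fisher: reject if the Fisher p-value is at most 0.05.
- Unconditional score: pooled Z statistic, with the p-value maximised over the common rate.
- Boschloo: the Fisher p-value used as the statistic, with its cut-off set so that the maximum size over the common rate is at most 0.05.

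Size at common rate p is Σₓ Σᵧ b(x; n₁, p) b(y; n₂, p) over rejected tables. Power is Σₓ Σᵧ b(x; n₁, p_OCS) b(y; n₂, p_Control) over rejected tables that favour OCS.

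*Size, 150 per arm.* Fisher: 3.4%, 3.6% and 3.7% at common rates of 15%, 20% and 25%, and at most 4.3%. Score: 4.8% at each of these rates, and at most 4.95% over all rates. At the unequal splits checked, Fisher's size at 20-25% is 4.2-4.3%.

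*Power (%), Control rate 25%, Fisher / score / Boschloo:*

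| OCS/Control n | OCS 20% (planned) | OCS 15% (assumed) |
|---|---|---|
| 150/150 | 14.6 / 17.3 / 16.8 | 52.9 / 57.7 / 56.7 |
| 145/145 | 14.0 / 16.5 / 15.9 | 51.5 / 55.9 / 54.8 |
| 148/152 | 16.7 / 17.4 / 18.2 | 56.9 / 58.0 / 59.1 |
| 152/148 | 15.2 / 17.5 / 16.7 | 54.3 / 58.2 / 56.5 |
| 153/147 | 16.3 / 17.7 / 17.8 | 56.6 / 58.2 / 58.9 |
| 143/147 | 16.4 / 16.5 / 17.5 | 55.5 / 55.9 / 57.3 |

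With 150 per arm, the score gain over Fisher is 4.4 points at an assumed OCS rate of 17%, peaks at 4.8 at 15%, and is 4.2 at 13%, 3.6 at 12% and 2.0 at 10%.

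*What changes in practice.* With 37 Control events in 150, Fisher needs 22 or fewer OCS events; both unconditional tests accept 23. For 23/150 v 37/150, Fisher p = 0.060 and unconditional score p = 0.045.

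*Nesting.* At 150, 145 and 144 per arm, every table Fisher rejects is also rejected by both unconditional tests. At 143/147, Fisher rejects four tables that the score test does not. Boschloo's test lost none of Fisher's rejections at any split checked. This follows from its construction: Fisher's rule already holds 5%, so Boschloo's cut-off cannot be stricter (for example 0.0562 at 148/152 and 0.0555 at 143/147).

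**The case against.** The strongest reply is that Fisher's test is valid, prespecified and stated identically in both documents. Superiority is a gated follow-on for which no power is promised, and at the planned rates neither test has a realistic chance. All of that stands. It makes this an optional efficiency gain rather than a correction.

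Some stronger readings are tempting, but the documents do not support them:
- *That the choice costs 4-5 points of power.* That needs equal arms, the score version and an assumed OCS rate of about 13-17% against 25%. At the plan's own rates with 150 per arm the score gain is 2.7 points. Per Protocol exclusions make exactly equal arms unlikely, and no unequal split checked reached 4 points.
- *That Fisher buys no protection.* Its actual false-positive rate is lower (3.7% against 4.8% for the score test at a rate of 25%). What it lacks is any protection the plan asked for beyond 5%.
- *That the planned interval can contradict the planned test because of Fisher.* SAP 12.1 gives only a one-sided 95% bound for the difference. For 24/150 v 37/150 the one-sided unconditional p is 0.034, so the bound lies below zero, while the two-sided p is 0.067 unconditional and 0.085 by Fisher. That mismatch comes from one-sided against two-sided levels and would remain after the change.
- *That the unconditional test with 135 per arm beats Fisher with 150.* At 15% v 25% this holds for equal arms (53.7% v 52.9%). In the unequal splits of 300 tried, Fisher has 54.3-56.9%.

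Timing is a fair worry. SAP 3.3 provides no blinding, and SAP 3.5 already counts 43 off-study transplants, so a late move to a less conservative test could look result-driven. This affects how and when the change is made.

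**Conclusion.** The point holds as an efficiency improvement on a follow-on claim. At the planned 20% v 25%, the gain over Fisher with 150 per arm is 2.2 points (Boschloo) or 2.7 (score), on a base of 14.6%. At an assumed 15% v 25% it is 3.8 or 4.8 points, on 52.9%. With arms a few patients apart, the gain at these rates is about 1 to 2.5 points (Boschloo) or 0 to 4 points (score). The gain was positive in every case computed, and size stayed within 5%. These figures rest on complete EAD data, the splits listed, and assumed OCS rates wherever they differ from 20%. No power was calculated here for the survival endpoints, so extending the change to SAP 12.2 rests on consistency alone. Fisher's test is not an error, and the primary non-inferiority conclusion does not depend on it.

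**What to change.** Before database lock, and before anyone sees comparative EAD results, replace Fisher's test for superiority in SAP 12.1 and 12.2 and protocol 9.3 with a two-sided exact unconditional test at 0.05. Boschloo's is preferable because it rejects whenever Fisher does; the unconditional score test is an acceptable alternative. State the test, the definition of two-sided and the maximisation over the common rate. Record the change and its date in SAP 3.5 as a departure from the protocol, and confirm there that no comparative results had been seen. SAP 5.3 separately gives normal-approximation superiority p-values after multiple imputation, so say which p-value decides the claim if outcomes are missing.

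The cost is some wording, documentation and a validated routine. Exact unconditional computation is already needed for the non-inferiority bound, but the documents do not show that Boschloo's test is programmed. The statistical price is a higher actual false-positive rate than Fisher's, still within 5%. If comparative EAD results have already been seen, keep Fisher's test as the declared test.

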6. ANALYSIS POPULATIONS

6.1. Per Protocol Population

The Per Protocol (PP) Population will consist of all randomized subjects who are transplanted and have no major protocol violations and for whom the donor liver received the complete preservation procedure as per the randomization assignment. The major protocol violations that will exclude a subject from this population are the following:

- Ineligible for the study according to the recipient inclusion and exclusion criteria
- Ineligible for the study according to the donor organ inclusion and exclusion criteria
- Subject is transplanted with a liver with preservation other than that to which the subject was randomized
- Failure to complete adequate post-transplant assessments to support the primary, secondary or safety endpoints
- Other major protocol violations

The final designation of major protocol violations resulting in an exclusion from the PP Population will be made during a blinded review by the CEC prior to database lock.

In analyses based on the PP Population, subjects will be analyzed as randomized. The primary analysis of the primary and secondary effectiveness endpoints and of other endpoints will be based on the PP Population.

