6.2. Modified Intent-to-Treat Population

The Modified Intent-to-Treat Population (mITT) will consist of all randomized subjects who are transplanted in the PROTECT study. In analyses based on mITT Population, subjects will be analyzed as randomized. The mITT Population analyses will be considered secondary analyses of effectiveness.

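### The superiority test, like the non-inferiority test, is judged first on the Per Protocol set, which drops recipients whose liver did not complete its assigned preservation; superiority should rest on mITT.

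*SAP*

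**What the plan says.** SAP 12.1 first tests non-inferiority against a margin of 0.075, using a one-sided 95% upper bound. It continues: "In the event non-inferiority is demonstrated, Fisher's exact test (two-sided) will be used to test for superiority". On the analysis sets it says "This endpoint will be analyzed using the Per Protocol and mITT Populations" and then "The Per Protocol analysis will be considered the primary analysis". No separate set is named for the superiority test. Protocol 9.3.1 has the same structure, and SAP 12.2 repeats it for the two survival endpoints.

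SAP 6.1 admits to the PP set only transplanted recipients "for whom the donor liver received the complete preservation procedure as per the randomization assignment". Its list of excluding violations includes "Subject is transplanted with a liver with preservation other than that to which the subject was randomized" and an open item, "Other major protocol violations". A blinded review by the clinical events committee (CEC) before database lock settles the exclusions. SAP 6.2 defines mITT as randomised recipients transplanted in the study, analysed as randomised, and ranks it lower: "The mITT Population analyses will be considered secondary analyses of effectiveness". Neither document requires mITT to agree before superiority is claimed.

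**The concern.** PP as the primary set is a common choice for non-inferiority. Superiority is a different question. There the comparison should keep the groups that randomisation formed, and a set that drops recipients because the assigned method was not completed does not.

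Completion of preservation is observed after randomisation and depends on how the method performs. The documents foresee such events. Protocol 9.4 lists device failure among the reasons for non-transplantation, protocol 9.2.3 deals with switchover, and SAP 6.3 and 6.4 deal with livers preserved partly by each method. The schedule in protocol Appendix 2 records device malfunction in the OCS column only. It is a reasonable inference that these exclusions would fall more on OCS, but it is an inference, since no failure or switchover rate is given.

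If the excluded OCS recipients had more EAD than those retained, the PP comparison would flatter OCS. A superiority statement could then appear in PP when the as-randomised comparison does not support it.

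**Working it through.** **The plan's own figure.** SAP 3.4 assumes EAD rates of 0.20 (OCS) and 0.25 (Control), margin 0.075, one-sided alpha 0.05 and 80% power, and states 144 per arm.
- Normal approximation: n = (1.645 + 0.842)² × (0.20×0.80 + 0.25×0.75) / (0.075 + 0.05)² = 6.183 × 0.3475 / 0.015625 = 137.5, so 138 per arm.
- Exact unconditional test on the Farrington-Manning statistic, as named in SAP 12.1: 80% power is first reached at 141 per arm, and power at 144 is 81.0%.

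The stated size is sound for non-inferiority. It was not chosen for superiority: with 150 per arm and the same rates, the two-sided Fisher test has about 15% power.

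**Room for exclusions.** SAP 3.4 enrols to 290 PP or 300 transplanted subjects, and needs 288. The implied allowance is 300 − 290 = 10 to 300 − 288 = 12 subjects.

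**How few exclusions could matter.** All counts below are assumed, with 150 per arm in mITT. Tests are two-sided Fisher at 0.05 (SAP 5.1). No Control recipient is excluded unless stated.

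| Case | OCS | Control | p |
|---|---|---|---|
| mITT | 30/150 | 43/150 | 0.106 |
| 3 OCS excluded, all with EAD | 27/147 | 43/150 | 0.041 |
| 3 excluded, 2 with EAD | 28/147 | 43/150 | 0.058 |
| 3 excluded, 1 with EAD | 29/147 | 43/150 | 0.079 |
| 3 excluded, none with EAD | 30/147 | 43/150 | 0.107 |
| 3 OCS and 1 Control excluded, all with EAD | 27/147 | 42/149 | 0.054 |

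Control here is 43/150 = 28.7%, above the planned 25%. With Control at 38/150 = 25.3%:

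| Case | OCS | Control | p |
|---|---|---|---|
| PP count as in the three-exclusion case | 27/147 | 38/150 | 0.16 |
| mITT | 27/150 | 38/150 | 0.16 |
| 4 OCS excluded, all with EAD | 23/146 | 38/150 | 0.045 |

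**False superiority in favour of OCS.** Let both true mITT rates be 0.25, let a share f = 0.04 of OCS recipients be excluded (6 of 150), and let e be the EAD rate among them. The rate among retained OCS recipients is (0.25 − f·e)/(1 − f). Full enumeration of the Fisher test with 144 v 150 gives:

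| e | Retained OCS rate | Chance of PP superiority for OCS |
|---|---|---|
| 0.25 | 0.250 | 2.1% |
| 0.50 | 0.240 | 3.4% |
| 0.75 | 0.229 | 5.2% |
| 1.00 | 0.219 | 7.8% |

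The nominal value in this direction is 2.5%. On mITT with 150 per arm the chance is 1.9%.

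**The case against.** The strongest reply is that superiority is subordinate and the plan is open about its sets. The primary hypothesis is non-inferiority. The sample size re-estimation, which could have enlarged the trial for superiority, was dropped (SAP 3.5). mITT results for the endpoint are tabulated, major violations leading to PP exclusion are reported by treatment group (SAP 8), organs not preserved as assigned are counted (SAP 7), and device malfunctions are reported as randomised (SAP 10). The CEC decides exclusions blinded and before lock. PP also excludes for ineligibility, inadequate assessments and other violations, which can arise in either arm.

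Much of this stands. A conflict between PP and mITT would be visible, and the low power makes a superiority claim unlikely at the planned rates. But visibility is not a decision rule, and the plan ranks PP first. Blinding guards against selective judgement; it cannot make the set neutral when failure of the assigned method is itself a ground for exclusion.

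Three stronger readings are tempting. One is that three exclusions are enough to reverse the result. That needs all three to have had EAD, no offsetting Control exclusion, and a Control rate above the planned one. Another is that exclusions will in fact concentrate in the OCS arm, which the documents give no rate to show. The third is that non-inferiority should have to succeed in both sets. Nothing computed here shows a non-inferiority conclusion changing, and PP as its primary set is a defensible trade-off.

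**Conclusion.** The point holds for the superiority test. As written, superiority can be claimed primarily on a set that omits recipients whose assigned preservation failed, and no rule lets mITT overturn it.

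The size is conditional. It depends on exclusions being unequal between arms and on excluded OCS recipients having more EAD than those retained. Under those assumptions, a few exclusions, within the allowance of 10 to 12, can move a non-significant mITT result to PP significance. With 4% of OCS recipients excluded, the chance of false superiority rises from 2.1% to between 3.4% and 7.8% as the EAD rate among the excluded goes from 50% to 100%. If their EAD rate equals that of the retained, there is no inflation. The documents do not show that such a bias will occur, and the non-inferiority design is not called into question.

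**What to change.** In SAP 12.1, state that the superiority test is carried out on mITT, as randomised, with PP as supportive, once non-inferiority has been shown. Keep PP primary for non-inferiority. Apply the same rule to the superiority tests in SAP 12.2. The practical effect there is small, because the SAP does not expect even non-inferiority on survival to be shown.

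Report PP exclusions by arm and reason, as SAP 8 largely provides, and add the EAD outcome of each excluded recipient.

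Record the change in SAP 3.5, because the protocol also makes PP primary. It should be settled before database lock.

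The cost is wording and one added listing. The mITT tables (2.1.2, 2.1.4, 2.3.2 and 2.3.4) are already planned, and the sample size does not change because it was set on non-inferiority. The downside is a somewhat lower chance of a superiority claim. The remedy is partial: mITT requires transplantation in the study, so livers lost before that, including through device failure, stay outside it.
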